The application of rTMS in pregnancy for the treatment of depression has resulted in two cases of inferior vena cava compression syndrome (also referred to as supine hypotensive syndrome) and one episode of dizziness without hypotension (Kim and Wang 2014). This condition typically occurs after 24 weeks gestation and is managed by placing the pregnancy women onto the left lateral position if they are going to be supine for an extended period of time. Thus, it has been recommended to avoid the supine position when applying rTMS to the pregnant women (Kim and Wang 2014). To decrease the likelihood of inferior vena cava compression syndrome, all subjects beyond 24 weeks gestation will be positioned on their left side using a wedge cushion.

Seizures can adversely affect pregnancy, and the use of high frequency stimulation, defined as greater than or equal to 10-Hz, in rTMS increases the risk of seizures. The general risk of seizures with rTMS is low (1/10,000), and rTMS has been used in pregnancy at high frequency (I.e. 25-Hz) stimulation without any adverse effects (Sayar *et al* 2014). The proposed study will utilize 5-Hz as it is the lowest, effective frequency stimulation reported for the treatment of neuropathic pain (Hosomi *et al* 2013). We believe this will minimize seizure risk, and in efforts to further decrease seizure risk with rTMS, the study is applying rTMS in trains of pulses interspersed with periods of rest and excluding those with risk factors for seizures. The results of the current study will provide data supporting the acceptability and feasibility of rTMS of the treatment of neuropathic pain in pregnancy and will support larger studies to determine the most effective and safe frequency stimulation for the treatment of neuropathic pain in pregnancy.

The management of chronic pain conditions in pregnancy has a direct effect on neonatal outcomes through fetal exposure. For example, neonatal abstinence syndrome is a drug withdrawal disorder of neonates that is secondary to in utero exposure to opioids, antidepressants, and muscle relaxants – all which are used to treat NP. Given the current limited knowledge of teratogenicity regarding pharmacological agents, we aim to better define the association of neonatal outcomes with chronic neuropathic conditions in pregnancy. **We aim to compare obstetrical and neonatal outcomes of pregnant women with neuropathic pain, non-neuropathic pain, and no pain.**

Objectives

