To further define the impact of NP in the peripartum period, we propose the following objectives:

- I. Characterize the course and pharmacological management of neuropathic pain in pregnancy and the postpartum period. We will define descriptive statistics of the use of analgesic medications in pregnancy and the postpartum period for the treatment of neuropathic pain.
- II. Compare obstetrical and neonatal outcomes of pregnant women with chronic neuropathic pain, non-neuropathic chronic pain, and pregnant women without chronic pain.
- III. Determine the acceptability and tolerability of rTMS for the treatment of neuropathic pain in pregnancy, and describe the impact of rTMS on neuropathic pain in pregnancy.

Subject Selection

Subjects will be enrolled through the Women's Mental Health Program (WMHP) at the University of Arkansas for Medical Sciences (UAMS) at the following clinical spaces: Psychiatric Research Institute (PRI); UAMS Women's Clinic (UWC); the Psychiatric Research Institute (PRI) inpatient units (PRI floors 5&6); and the UAMS Obstetrics & Gynecology units (UAMS floors 5,6, and 7A).

Protocol Title: Neuropathic Pain in Pregnancy
Institution: University of Arkansas for Medical Sciences (UAMS)
IRB Number: 204737
Sponsor: UAMS
PI: [name]

Study visits can occur at all of the above locations. For those subjects in part B, study visits will occur in a designated room designed for rTMS in the PRI. We aim to actively recruit and enroll 60 pregnant women and up to 70 infants (to allow for multiple gestation pregnancies) for Part A of this study and enroll 10 pregnant women and up to 15 infants (to allow from multiple gestation pregnancies) (from Part A) for Part B.

Compensation: Mothers participating in the study will receive a \$10 in cash for each visit. All participants will be given a token or voucher to pay for parking at each outpatient study visit when applicable.

Inclusion of Women, Minorities and Children

Women and adolescents between 18-45 years of age are eligible for participation in the current study. Every effort will be made to recruit a diverse population of women along racial and ethnic categories residing in underserved areas.

Eligibility Criteria

All women will provide consent and HIPAA authorization prior to enrollment in the study.

Part A:

Maternal Inclusion Criteria

- Age 18-45 years old,
- Ability to give informed consent,
- Viable pregnancy, and
- Enrollment prior to or equal to 24 weeks gestation

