
• Preterm labor• Preterm birth• Premature rupture of membranes• Mode of delivery	
• 1 minute and 5 minute APGAR Scores• Length of Hospitalization• Neonatal Intensive Care Unit Admission• Neonatal Abstinence Syndrome• Birth weight and length• Gender

Part B (rTMS):

We will determine the acceptability of rTMS as a treatment option by determining the percentage of subjects who accept the treatment when offered. Tolerability will be determined by the reporting of adverse events. The primary outcome measure is VAS. Secondary outcome measures include BDI, PGIC, and CGI-I. For each outcome measure, scatter plots will be constructed for visual inspection across treatment. Using previous studies of rTMS for the treatment of neuropathic pain, we will determine an effect size and complete a power analysis. This information will help guide future studies of the effectiveness of rTMS in the treatment of neuropathic pain in pregnancy.

Neonatal outcomes will be analyzed between the following groups: 1. Subjects participating in rTMS (Part B); 2. Subjects with neuropathic pain who participated in Part A but did not participate in Part B; 3. Subjects with chronic non-neuropathic pain who participated in Part A; and 4. Subjects without chronic pain who participated in Part A. Specific endpoints of interest include neonatal intensive care unit admission, length of hospitalization, birth weight and length, and 1-min and 5-min APGAR scores. The occurrence of obstetrical outcomes will be compared between the groups. If measures are normally distributed, we will use ANOVA to test the differences among the three groups. Otherwise, we will use a non-parametric method, such as Kruskal Wallis test, to test the difference among the groups.

Neonatal outcomes will be scrutinized after each delivery and neonatal period. The investigator team will convene and review all neonatal outcomes to determine if any complication occurred that could be attributed to the study, participation in the study, and/or treatment received. If any complication is identified (i.e. preterm delivery with all subjects who participated in rTMS), we will cease all current and potential study procedures related to part B of the study.

All statistical analysis will be completed using SAS 9.4. Significance will be set at $p<0.05$.

Data Safety and Monitoring Plan

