Table 3 provides a list of specific outcome data of interest for the second hypothesis. The occurrence of obstetrical outcomes will be compared between the three groups. If measures are normally distributed, we will use ANOVA to test the differences among the three groups. Otherwise, we will use a non-parametric method, such as Kruskal Wallis test, to test the difference among the groups.

Table 3: Specific Outcome Data

Obstetrical Records	Neonatal Records

• Preterm labor• Preterm birth• Premature rupture of membranes• Mode of delivery	
• 1 minute and 5 minute APGAR Scores• Length of Hospitalization• Neonatal Intensive Care Unit Admission• Neonatal Abstinence Syndrome• Birth weight and length• Gender

Part B (rTMS):

We will determine the acceptability of rTMS as a treatment option by determining the percentage of subjects who accept the treatment when offered. Tolerability will be determined by the reporting of adverse events. The primary outcome measure is VAS. Secondary outcome measures include BDI, PGIC, and CGI-I. For each outcome measure, scatter plots will be constructed for visual inspection across treatment. Using previous studies of rTMS for the treatment of neuropathic pain, we will determine an effect size and complete a power analysis. This information will help guide future studies of the effectiveness of rTMS in the treatment of neuropathic pain in pregnancy.

Protocol Title: Neuropathic Pain in Pregnancy
Institution: University of Arkansas for Medical Sciences (UAMS)
IRB Number: 204737
Sponsor: UAMS
PI: [name]

Neonatal outcomes will be analyzed between the following groups: 1. Subjects participating in rTMS (Part B); 2. Subjects with neuropathic pain who participated in Part A but did not participate in Part B; 3. Subjects with chronic non-neuropathic pain who participated in Part A; and 4. Subjects without chronic pain who participated in Part A. Specific endpoints of interest include neonatal intensive care unit admission, length of hospitalization, birth weight and length, and 1-min and 5-min APGAR scores. The occurrence of obstetrical outcomes will be compared between the groups. If measures are normally distributed, we will use ANOVA to test the differences among the three groups. Otherwise, we will use a non-parametric method, such as Kruskal Wallis test, to test the difference among the groups.

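### The only comparative analysis of infant and obstetrical outcomes after rTMS is a significance test with about 10 treated women; it needs between-group estimates with intervals, because a null test alone cannot separate no harm from undetectable harm

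*Protocol*

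**What the plan says.** The Part B analysis text is the same in the Protocol (Statistical Methods and Data Management, Part B) and the SAP (Part B). It reads "Neonatal outcomes will be analyzed between the following groups: 1. Subjects participating in rTMS (Part B", followed by women with neuropathic pain who did not enter Part B, women with non-neuropathic pain, and women without pain. The endpoints are NICU admission, length of stay, birth weight, birth length and the two APGAR scores. Obstetrical outcomes are compared in the same way.

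The method is ANOVA if the data are normal. The alternative is "Otherwise, we will use a non-parametric method, such as Kruskal Wallis test, to test the difference among the groups". The reading rule for all analyses is "All statistical analysis will be completed using SAS 9.4. Significance will be set at $p<0.05".

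On size, Protocol, Subject Selection, says "We aim to actively recruit and enroll 60 pregnant women and up to 70 infants" for Part A and "enroll 10 pregnant women and up to 15 infants (to allow from multiple gestation pregnancies) (from Part A) for Part B".

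Three other provisions bear on infant safety:
- The same Part B text has the team review neonatal outcomes after each delivery and cease Part B if an attributable complication is found.
- Protocol, Independent Study Monitoring, has the medical monitor review adverse events after every three Part B enrollments.
- Under Part A, both documents plan descriptive statistics for all measures. Delivery and neonatal records are Part A measures (Protocol, Table 1).

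Neither document gives a between-group estimate, confidence interval, bound, margin, harm size or power for the comparison that includes the rTMS group.

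**The concern.** The case reviews and the monitor's review have no comparator, and the descriptive summaries give no contrast with its uncertainty. The four-group test is therefore the only place where outcomes after rTMS are set against outcomes without it, and a p-value is the only result specified there.

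With about 10 treated women, a p-value above 0.05 is what one expects both when rTMS does no harm and when it does a moderate amount. An interval from the same data shows which harms are excluded and which are not. That matters for a study described as the first pilot of rTMS for neuropathic pain in pregnancy, whose results are meant to inform larger studies.

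**Working it through.** The documents state no power, SD or effect size for this comparison, so there is no figure of theirs to reproduce.

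**Inputs from the documents:** 60 women, 10 of them treated with rTMS, so 60 − 10 = 50 untreated; four groups; alpha 0.05.

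**Assumptions:** one infant per woman, all records available, the three untreated groups equal to each other, and a harm of d SD in the rTMS group only. The values of d, the 10% background NICU rate and the split of the 50 untreated women are not in the documents.

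**1. Four-group ANOVA.** The noncentrality is λ = d² × 10 × 50 / 60. The critical F on 3 and 56 degrees of freedom is 2.77. With the untreated groups equal, the result does not depend on how the 50 women split.

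| Assumed harm | λ | Power | Missed |
|---|---|---|---|
| 0.3 SD | 0.75 | 9.5% | 90.5% |
| 0.5 SD | 2.08 | 18.8% | 81.2% |
| 0.8 SD | 5.33 | 43.9% | 56.1% |
| 1.0 SD | 8.33 | 64.0% | 36.0% |

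Power reaches 80% only at about 1.19 SD. Simulation at 0.5 SD (groups 10/10/20/20) gives 18.6% for ANOVA and 16.8% for Kruskal-Wallis.

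**2. Sensitivity at 0.5 SD.** Missed:
- 10 v 10 by t-test: 81.5%
- 10 v 20: 76.1%
- 10 v all 50 pooled: 70.5%
- three groups of 10/25/25: 77.7%
- 15 treated infants of 70, taken as independent: 74.4%
- records for only 8 treated and 40 untreated: 84.5%
- 10 v only 5 untreated women with neuropathic pain: 86.5%

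The range is therefore roughly 70 to 85%, slightly higher if the neuropathic comparator is very small.

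**3. NICU admission by Kruskal-Wallis (simulation, groups 10/10/20/20 and 10/20/15/15).** A rise from an assumed 10% to 30% is missed 73–75% of the time, and a rise from 10% to 40% about 53%.

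**4. What intervals from the same data would show.**
- No events in n pregnancies: the exact two-sided 95% upper limit is 1 − 0.025^(1/n). For n = 10 it is 30.8%; for n = 8 it is 36.9%.
- 1 of 10 in each of two groups: the Wilson limits are 1.8% and 40.4%, so the Newcombe half-width is √[(0.100 − 0.018)² + (0.404 − 0.100)²] = 0.315. The risk difference runs from −32 to +32 points.
- Mean difference: the 95% half-width is t × √(1/10 + 1/n₂) SD. For 10 v 10 it is 2.101 × 0.447 = 0.94 SD; for 10 v 20 it is 2.048 × 0.387 = 0.79 SD.

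**The case against.** The strongest case against has four parts.

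**Infant harm is not left to a p-value.** Each delivery is reviewed, Part B can be ceased without any test, and a medical monitor looks at adverse events. This stands. A reader might infer that p<0.05 is the plan's only safety criterion, and the documents do not support that. These provisions have no comparator, though, so they do not supply the missing estimate.

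**The plan claims no safety from a null test.** This also stands. Objective III covers acceptability, tolerability and the effect on pain. A reader might take the background statement that the results "will support larger studies to determine the most effective and safe frequency stimulation for the treatment of neuropathic pain in pregnancy" as carrying a null result forward as evidence of safety. The sentence offers data on acceptability and feasibility and leaves the safe frequency for the larger studies to establish, so it defers safety.

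**Descriptive statistics are planned.** They are, and it would be wrong to say that nothing but p-values will appear. The gap is narrower: no difference between rTMS and a comparator, and no interval.

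**A pilot is small by design, and large harms may be seen.** Small size is not the fault here. A 1.0-SD harm is detected 64% of the time under the assumptions above, so a null result is likely only for smaller harms. The miss rates are also per endpoint, and several endpoints are tested. None of this tells the reader of a null result which harms remain possible.

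**Conclusion.** The point holds as a gap in how one comparison is to be read. The only comparative analysis of neonatal and obstetrical outcomes after rTMS is a test at p<0.05 with about 10 treated women, and no estimate or interval accompanies it. A null result could not be told apart from a harm the study was unable to detect.

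The size depends on assumed harms: about 81% missed at 0.5 SD, 56% at 0.8 SD and 36% at 1.0 SD. These figures rest on full recruitment, complete records and equal untreated groups. Protocol, Investigational Plan, obtains delivery and neonatal records only for births at the study institution, so the number analysed may be smaller.

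It does not follow that the plan leaves infants unmonitored, or that the sponsor intends to declare rTMS safe from a null test. The change is worth making because it is nearly free and alters what the pilot can legitimately report.

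**What to change.** In the Part B analysis text of both Protocol and SAP, make estimation the primary reading of this comparison:

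1. Name the untreated women with neuropathic pain (group 2) as the main comparator, with the other two groups shown alongside.
2. For each binary endpoint, and each category of mode of delivery, give the rTMS count with an exact (Clopper-Pearson) 95% interval and the risk difference with a Newcombe 95% interval.
3. For birth weight and length give the mean difference, and for length of stay and APGAR the Hodges-Lehmann shift, each with a 95% interval.
4. Count per pregnancy (for example, any infant affected, or one value per mother), or use an interval that allows for twins. State how many pregnancies have records.
5. Add wording such as: *P-values for these endpoints are descriptive. A non-significant result will not be interpreted as absence of harm. Where no event occurs, the exact upper 95% limit for the number of pregnancies actually observed will be reported (30.8% for 0 of 10, 36.9% for 0 of 8).*

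The per-delivery review, the rule to cease Part B and the monitor's review are untouched. The cost is wording in two documents and a little more SAS programming, with no new data, visits or participants. The drawback is that the intervals will be wide, so the safety message will look less favourable than a list of non-significant tests.

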Maternal Exclusion Criteria

- Active or history of substance use disorder within the past year
- Non-English speaking

Part B:

Maternal Inclusion Criteria

- Subjects enrolled in Part A and willing to consent to Part B of this protocol
- Pregnant with current chronic neuropathic pain
- Subjects failed treatment with amitriptyline or nortriptyline as defined by one of the following:
 - no clinical improvement following a four week trial of amitriptyline or nortriptyline (i.e., CGI-I score ≥ 4)
 - an inability to tolerate the medication (i.e., side effects)
- Subjects must pass the TMS Safety Checklist Adult Safety Screen (TASS).
- Subjects should be off medication, which can lower seizure thresholds (e.g., amitriptyline and nortriptyline) for at least two weeks prior to study entry.
- Subjects with neuropathic pain including those with diagnosis of spinal cord injury, fibromyalgia, compression neuropathies (including diabetic peripheral neuropathy), post stroke pain, and multiple sclerosis
- Subjects with a baseline VAS score greater than 30

Protocol Title: Neuropathic Pain in Pregnancy
Institution: University of Arkansas for Medical Sciences (UAMS)
IRB Number: 204737
Sponsor: UAMS
PI: [name]

Maternal Exclusion Criteria

- Current or past history of a seizure disorder (e.g., epilepsy)
- Current history of preeclampsia
- Current or history of brain lesions (e.g., aneurysm)
- History of major head trauma (e.g., stroke; previous cranial neurosurgery)
- Ferromagnetic metal in the head, neck, or chest (e.g., plates or pins, bullets, shrapnel)
- Microprocessor implants in the head (e.g., cochlear implants) or life-sustaining microprocessor implants anywhere in the body (e.g., prosthetic cardiac valves)
- Cardiac pacemaker
- Active or inactive implants (e.g., deep brain stimulators, vagus nerve stimulators)
- Active treatment with medications that lower seizure threshold (e.g., bupropion, amitriptyline, nortriptyline, or other TCA)
- Increased intracranial pressure (which lowers seizure threshold)
- Implanted medication pumps
- Intracardiac lines
- Significant heart disease defined as heart disease that causes moderate to severe symptoms and/or is characterized by moderate to severe pathology, including a recent history of myocardial infarction and heart failure with an ejection fraction of less than 30% or with a New York Heart Association Functional Classification of Class III or IV.
- Bipolar disorder (to reduce the risk of mania)

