prescription and non-prescription medications used in pregnancy and the postpartum period. A urine drug screen will also be obtained at each visit testing for the presence or absence of the following: amphetamines/methamphetamines, barbiturates, benzodiazepines, THC, cocaine, methadone, opiates, PCP, and cotinine. For all visits following entry visit, subjects will complete the Patients' Global Impression of Change scale (PGIC) (Hurst and Bolton 2004); and the clinician will complete the Clinical Global Impression-Global Improvement scale (CGI-I) (Guy 1976). At all study visits, weight and vital signs will be collected. For all subjects who delivered at UAMS, medical records for labor and delivery and neonatal outcome will be obtained following birth. All subjects will participate in Part A. All subjects will receive treatment as usual within each group.

Part B:

Subjects in group 1 will be invited to participate in part B of the study following their enrollment in part A. This pilot study will aim to enroll 10 subjects (of Group A).

Subjects will undergo daily rTMS, defined as Monday through Friday, for a total of 10 consecutive sessions with the exception of weekends and holidays (i.e., Monday to Friday only). Typically, a stimulation period will start on Monday (day 1) and end on Friday (day 12). In the case that a stimulation period does not start on Monday, day 1 will begin on the day of the subject's first rTMS session. Subjects will be followed daily until day 29, following their last session of rTMS (day 12). Table 2 provides an overview of study procedures. For each session (days 1-5 and 8-12), subjects will complete a VAS prior, immediately following, and 60 minutes post. Adverse events will also be recorded prior to and immediately following and 60 minutes after each session. They will complete a BDI on Days 1, 5, 12, 22, and 29. Subjects will complete VAS also on days 22 and 29. For days 5, 12, 22, and 29; subjects will complete the PGIC; and clinicians will complete the CGI-I. Subjects will have a maximum of 12 visits for Part B (10 rTMS sessions plus days 22 and 29). Either study visit for days 22 or 29 may occur in conjunction with a study visit for Part A.

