Rare: Seizure and hearing loss. The risk of having a single seizure is small, estimated at $\leq 1/10,000$ (Rossi *et al* 2009). In order to decrease this risk, subjects with preeclampsia, brain lesions, head trauma, a history of seizures (e.g., epilepsy), or taking medications known to lower seizure threshold are precluded from participating in rTMS. Study staff administering rTMS are trained in the treatment and management of an acute seizure. Life-support equipment is also readily available. All subjects will be visually monitored for signs of a seizure and/or muscle twitching throughout each rTMS treatment.

Another risk is hearing loss (temporary or permanent). To minimize this risk, subjects will wear ear plugs during rTMS. Subjects will be asked to immediately report any loosening or detachment of an earplug during treatment. Study staff will immediately stop rTMS if a subject reports or if an investigator observes that a subjects' ear plug has loosened or has fallen out.

Rare: A specific, but rare, risk of rTMS in pregnancy is inferior vena cava syndrome (or supine hypotensive syndrome). This syndrome happens in pregnancy after 24 weeks pregnant and usually occurs after laying down for about 5-10 minutes. Common symptoms are feeling dizzy

Protocol Title: Neuropathic Pain in Pregnancy
Institution: University of Arkansas for Medical Sciences (UAMS)
IRB Number: 204737
Sponsor: UAMS
PI: [name]

and/or upset to your stomach and having low blood pressure and/or high heart rate. The symptoms do not last long and usually go away when you change your position, such as lay on your left side. To decrease the chance of this happening, you will have a cushion placed under your right side during treatments when you are 24 weeks pregnant or greater.

Temporary changes in vision may be noticed immediately after rTMS. These visual changes are not thought to be actual problems with the eyes, but, rather changes in brain functioning as a result of rTMS. Things like blurred vision and/or eye floaters normalize in time. The risk will be minimized by using conservative stimulation parameters.

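### The neonatal comparison of rTMS with untreated neuropathic women leaves deliveries and preeclampsia before possible Part B entry in the comparator only, so this component favours rTMS by an amount the documents do not fix

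*Protocol*

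**What the plan says.** The Part B (rTMS) paragraphs of Statistical Methods and Data Management, identical in protocol and SAP, set up four groups for neonatal outcomes. Group 1 is the rTMS participants. Group 2 is "Subjects with neuropathic pain who participated in Part A but did not participate in Part B". Groups 3 and 4 are the Part A women with chronic non-neuropathic pain and without chronic pain. The endpoints are NICU admission, length of hospitalization, birth weight and length, and 1- and 5-minute APGAR scores. Obstetrical outcomes are compared as well, and Table 3 lists preterm birth among them. The test is ANOVA, or a non-parametric test such as Kruskal-Wallis.

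Entry to the two parts differs in time and in conditions:

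- Part A (Eligibility Criteria): "Enrollment prior to or equal to 24 weeks gestation". Its two exclusions concern substance use disorder and language; preeclampsia is not among them.
- Part B timing (Investigational Plan): "Subjects in group 1 will be invited to participate in part B of the study following their enrollment in part A". No gestational-age window is given.
- Part B inclusion: "Pregnant with current chronic neuropathic pain"; failed tricyclic treatment, meaning either "no clinical improvement following a four week trial of amitriptyline or nortriptyline" or intolerance; at least two weeks off medication that can lower the seizure threshold; baseline VAS above 30.
- Part B exclusion: "Current history of preeclampsia". The section on rTMS risks repeats it, naming "subjects with preeclampsia, brain lesions, head trauma, a history of seizures" among those precluded.

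**The concern.** Membership of group 2 is settled only in retrospect, by a woman never having entered Part B. One way never to enter is to deliver first, or to develop preeclampsia first. Such a woman is placed in group 2 because of an event that is itself an outcome (preterm birth) or drives the listed ones (NICU stay, birth weight). The rTMS group cannot hold a case of this kind, since every member had passed that point when she started. This is immortal-time bias with an eligibility restriction added. Groups 3 and 4 have the same asymmetry against rTMS.

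The protocol describes the study as the first pilot of rTMS for neuropathic pain in pregnancy, and group 2 is its only comparator with the same condition and no rTMS. Preterm delivery is also the protocol's own example of a complication that would stop Part B.

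**Working it through.** **No stated figure to reproduce.** The documents give no event rate, effect size or power for this comparison. The check is logical first, then illustrative.

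**Step 1: who can hold a pre-entry event.** Let *a* be gestational age at Part A entry and *s* the age at which a woman could first start rTMS. For a delivery or preeclampsia onset between *a* and *s*:

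- rTMS group: impossible, by the pregnancy inclusion and the preeclampsia exclusion.
- Group 2, and groups 3 and 4 over the same weeks: possible, and counted.

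Preeclampsia arising after Part B entry still counts in the rTMS group. Neither document sets a landmark, matches on gestational age, treats rTMS as time-varying or adjusts for a covariate.

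**Step 2: how long the interval can be.** If the four-week trial and the two weeks off both follow Part A entry, *s* − *a* is at least 4 + 2 = 6 weeks. Entry at 24 weeks then gives *s* of at least 30 weeks; entry at 18 weeks gives at least 24. If the tricyclic had already failed and been stopped, the interval can be close to zero. Two features suggest that some waiting is expected: in Part A the CGI-I, which defines non-response, is collected only after the entry visit, with visits 4 to 6 weeks apart; and the protocol describes positioning for rTMS beyond 24 weeks, past the Part A entry limit.

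**Step 3: illustrative size with no true rTMS effect.** Assumed, not in the documents: Part A entry uniform over 10 to 24 weeks; preterm risk 10 to 20%; preterm deliveries split 6% at 24–28 weeks, 11% at 28–32, 13% at 32–34 and 70% at 34–37; preeclampsia 5 to 10%, starting 0 to 4 weeks before delivery, with four times the preterm risk; half of eligible women take rTMS. The ratio is risk in the rTMS group divided by risk in group 2 as written.

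| Wait from Part A to rTMS | Ratio, preterm birth | Ratio, delivery before 34 weeks | Expected pre-entry deliveries or preeclampsia per 20 neuropathic women |
|---|---|---|---|
| none | 1.00 | about 1.0 | about 0 |
| 6 weeks | 0.95–0.96 | 0.84–0.85 | 0.05–0.11 |
| 6–12 weeks | 0.86–0.88 | 0.62–0.65 | 0.16–0.35 |
| 6–16 weeks | 0.73–0.77 | 0.48–0.51 | 0.5–0.9 |

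The last column assumes 20 women in the neuropathic group (10 with rTMS, 10 without); the documents do not state that group's size.

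With preterm risk 15%, preeclampsia 8% and a 6–12 week wait, the preterm rates are 13.9% (rTMS) and 16.0% (group 2), so 13.9/16.0 = 0.87. At 30% and 80% uptake the ratio is 0.90 and 0.73.

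**Step 4: does alignment remove it?** In the same example, a comparator restricted to women still pregnant and preeclampsia-free at the matched entry time also has 13.9% preterm, against 13.9% for rTMS. The spurious gap disappears.

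**Step 5: what one case does.** With an assumed 10 women in group 2, one pre-entry event moves its rate by 1/10 = 10 percentage points. Even 0/10 against 3/10 gives Fisher p = 0.21, so the comparison carries little inferential weight either way.

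**The case against.** The strongest reply is that the effect may be very small. The 24-to-30-week case is the latest entry; a woman who joins by 18 weeks with a 6-week run-in starts by 24 weeks, before almost any live birth. The tricyclic failure need not fall within Part A, and the intolerance route needs no four-week trial. At a 6-week wait, the last column of the table implies that only about one trial in nine, at most, would contain a single such case. All of this stands. It limits the size but leaves the mechanism in place, and the documents do not rule out longer waits.

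A reader might infer more: that the plan makes rTMS look safer than it is, or could hide fetal harm. The documents do not support that.

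- rTMS women must be treatment failures with VAS above 30, and group 2 women need not be. That selection could push outcomes the other way, so the net direction is not determined.
- Safety review does not rest on group 2. Both documents have the investigators review neonatal outcomes after each delivery, with cessation of Part B if an attributable complication is found. The protocol adds a meeting with the medical monitor after every 3 Part B enrolments.
- No passage makes the contrast with group 2 the basis for a conclusion on fetal safety. The rTMS objective concerns acceptability, tolerability and impact on pain.

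**Conclusion.** The concern holds in a limited form. As written, deliveries and preeclampsia between Part A enrolment and possible Part B entry can fall only in the comparators, and this component favours rTMS on preterm birth and, through early delivery and preeclampsia, on NICU admission, birth weight and length of stay. That follows from the documents alone. The size does not: it is near zero with immediate entry and grows with later entry, and every ratio in the table rests on assumed event rates, uptake and waits. The net direction of all selection effects is unknown. With about 10 rTMS women the comparison is mainly descriptive. The change is still worth making, because it is cheap and a table this small is easily distorted by one misplaced case.

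**What to change.** In the Part B (rTMS) paragraphs of both documents, for contrasts with rTMS:

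1. Limit group 2 to neuropathic women who never received rTMS and who were still pregnant, with no recorded preeclampsia, at a gestational-age landmark taken from the rTMS women's session 1. For example, assign each comparator once to one rTMS woman's start week. No woman is then counted twice, and the groups stay independent, as ANOVA and Kruskal-Wallis require.
2. Apply the same landmark to groups 3 and 4 when they are compared with rTMS.
3. Report gestational age at session 1, and show the unrestricted groups descriptively.
4. List separately the neuropathic women who delivered or developed preeclampsia before they could enter Part B.

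This changes analysis wording only and adds no visits. The costs are a somewhat smaller comparator and reliance on visit and delivery records to date preeclampsia. Its onset date is not a listed data item, and delivery records are promised only for women who deliver at the study institution. Requiring that comparators never receive rTMS still uses later information; that is accepted so that no woman appears on both sides. The landmark does not address selection on tricyclic failure or VAS, which should be stated as a limitation.
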